4.5.7.2 Tumor Biopsy at the Time of Disease Recurrence

Biopsy at the time of first radiographic confirmation of disease recurrence is mandatory for all randomized patients (in both Arms A and B). Biopsy can only be waived for patients who have no lesions amenable for biopsy at disease recurrence, following discussion with and approval by the Medical Monitor. *After the primary analysis, a confirmatory tumor biopsy is optional at the time of disease recurrence.*

Acceptable samples include resections; core needle biopsies for deep tumor tissue or lymph nodes; or excisional, incisional, punch, or forceps biopsies for cutaneous, subcutaneous, or mucosal lesions. For core needle biopsy specimens, at least three cores should be submitted for evaluation.

The status of immune-related and tumor type–related, and other exploratory biomarkers (including but not limited to T-cell markers and tumor mutation status) in tumor tissue samples of enrolled patients may be evaluated.

Next-Generation Sequencing (NGS) may be performed by Foundation Medicine. If performed by Foundation Medicine, the investigator can obtain results from the

samples collected at the time of disease recurrence in the form of an NGS report, which is available upon request directly from Foundation Medicine. The investigator may share and discuss the results with the patient, unless the patient chooses otherwise. The Foundation Medicine NGS assay has not been cleared or approved by health authorities. The NGS report is generated for research purposes and is not provided for the purpose of guiding future treatment decisions.

4.5.7.3 Use and Storage of Remaining Samples from Study-Related Procedures

The remaining samples obtained for study-related procedures will be destroyed no later than 5 years after the end of the study or earlier depending on local regulations. If the patient provides optional consent for storing samples into the RCR for future research (see Section 4.5.12), the samples will be destroyed no later than 15 years after the date of final closure of the clinical database.

4.5.8 Anti-Therapeutic Antibody Testing (Atezolizumab-Treated Patients Only)

Atezolizumab may elicit an immune response. Patients with signs of any potential immune response to atezolizumab will be closely monitored. Validated screening and confirmatory assays will be employed to detect ATAs at multiple timepoints before, during, and after treatment with atezolizumab (see Appendix 2 for the schedule). The immunogenicity evaluation will utilize a risk-based immunogenicity strategy (Rosenberg et al. 2004; Koren et al. 2008) to characterize ATA responses to atezolizumab in support of the clinical development program. This tiered strategy will include an assessment of whether ATA responses correlate with relevant clinical endpoints. Implementation of ATA characterization assays will depend on the safety profile and clinical immunogenicity data.

4.5.9 Electrocardiograms

A twelve-lead ECG is required at screening and when clinically indicated during study. ECGs for each patient should be obtained from the same machine wherever possible. ECG recordings must be performed after the patient has been resting in a supine position for at least 10 minutes.

For safety monitoring purposes, the investigator must review, sign, and date all ECG tracings. Paper copies of ECG tracings will be kept as part of the patient's permanent study file at the site. Any morphologic waveform changes or other ECG abnormalities must be documented on the eCRF.

4.5.10 Patient-Reported Outcomes

The EQ-5D-5L is a generic preference-based HRQoL questionnaire that provides a single index value for health status (see Appendix 8) and is used to inform pharmacoeconomic evaluations and to measure general health status. The EQ-5D-5L consists of two parts; the first part, health state classification, contains five dimensions of

health: mobility, self-care, usual activities, pain/discomfort, and anxiety/depression. From these five items, a utility measure is obtained for each patient. The second part, consisting of a visual analog scale (VAS), allows the patient to indicate, on a scale of 0–100, how his or her health is on the day of assessment, with 100 being the “best imaginable health state” and 0 being the “worst imaginable health state.” The VAS score will be used as a measure of overall health status.

The EQ-5D-5L will be administered every 6 weeks during study treatment/observation. After discontinuation of the treatment/observation period, for patients who have not experienced disease recurrence, the EQ-5D-5L will be administered at the same schedule as the assessments for disease recurrence (see Section 4.5.5). The EQ-5D-5L will also be recorded (in both study arms) at 6, 12, and 24 weeks after occurrence of a DFS event. *After the primary analysis, the EQ-5D-5L assessments are no longer required for patients who are in disease recurrence follow-up or who have had a DFS event.*

During study treatment/observation, the EQ-5D-5L will be administered at the study sites. The PRO questionnaires, translated as required in the local language, will be distributed by the investigator’s staff and completed in their entirety by the patient. To ensure instrument validity and that data standards meet health authority requirements, PRO questionnaires filled out at the study sites should be self-administered at the investigational site prior to the completion of other study assessments and the administration of study treatment. Study personnel should review all questionnaires for completeness before the patient leaves the investigational site. Hard copy originals of the questionnaires must be maintained as part of the patient’s medical record at the site for source data verification. These originals should have the respondent’s initials on each page in compliance with good clinical practices.

Assessments of the EQ-5D-5L at 6, 12, and 24 weeks after a DFS event will be administered by telephone. Interviews will be conducted by trained site staff and in compliance with best practices and recommendations by EuroQol. Study personnel will record patient responses on a paper copy of the EQ-5D-5L during the telephone interview as record of source documentation. *After the primary analysis, the EQ-5D-5L assessments are no longer required for patients who have had a DFS event.*

4.5.11 Age-Adjusted Charlson Comorbidity Index (ACCI)

ACCI (see [Appendix 4](#)) is a significant independent predictor for OS and for cancer-specific mortality following radical cystectomy in multivariate analysis that included other clinicopathologic features (Koppie et al. 2008; Mayr et al. 2012). A baseline ACCI should be determined for every patient.

4.5.12 Optional Biopsies and Samples for Roche Clinical Repository (Optional Future Research)

4.5.12.1 Overview of the Roche Clinical Repository

The RCR is a centrally administered group of facilities used for the long-term storage of human biologic specimens, including body fluids, solid tissues, and derivatives thereof (e.g., DNA, RNA, proteins, peptides). The collection and analysis of RCR specimens will facilitate the rational design of new pharmaceutical agents and the development of diagnostic tests, which may allow for individualized drug therapy for patients in the future.

Specimens for the RCR will be collected from patients who give specific consent to participate in this optional research. RCR specimens will be used to achieve the following objectives:

- To study the association of biomarkers with efficacy, adverse events, or disease recurrence
- To increase knowledge and understanding of disease biology
- To study drug response, including drug effects and the processes of drug absorption and disposition
- To develop biomarker or diagnostic assays and establish the performance characteristics of these assays

4.5.12.2 Approval by the Institutional Review Board or Ethics Committee

Collection and submission of biological samples to the RCR is contingent upon the review and approval of the exploratory research and the RCR portion of the Informed Consent Form by each site's Institutional Review Board or Ethics Committee (IRB/EC) and, if applicable, an appropriate regulatory body. If a site has not been granted approval for RCR sampling, this section of the protocol (Section 4.5.12) will not be applicable at that site.

4.5.12.3 Sample Collection

The following samples will be collected for research purposes, including but not limited to research on dynamic (non-inherited) biomarkers:

- Remaining blood derivatives (serum, plasma, PBMCs and their derivatives) after study-related tests have been performed
- Remaining FFPE tissue (with the exception of archival FFPE blocks, which will be returned to sites) after study-related tests have been performed
- Optional tissue samples collected for biopsy during the study (preferably at the time of disease recurrence)

The following samples will be collected for research purposes, including but not limited to research on genetic (inherited) biomarkers:

- Whole blood sample for DNA isolation

This sample will be collected from patients who have consented to optional RCR sampling at baseline as shown in the schedule of assessments in [Appendix 1](#). If, however, the RCR genetic blood sample is not collected during the scheduled visit, it may be collected as soon as possible (after randomization) during the conduct of the clinical study. Collection of whole blood will enable the evaluation of single nucleotide polymorphisms in genes associated with immune biology including but not restricted to the target and pathway associated genes such as PD-L1, PD-1, and B7.1 as well as IL-8, IL-6, and related cytokines. The sample may be processed using techniques such as kinetic PCR and DNA sequencing.

For all samples, dates of consent should be recorded on the associated RCR page of the eCRF. For sampling procedures, storage conditions, and shipment instructions, see the laboratory manual.

RCR specimens will be destroyed no later than 15 years after the date of final closure of the associated clinical database. The RCR storage period will be in accordance with the IRB/EC-approved Informed Consent Form and applicable laws (e.g., health authority requirements).

The dynamic biomarker specimens will be subject to the confidentiality standards described in Section [8.4](#). The genetic biomarker specimens will undergo additional processes to ensure confidentiality, as described below.

4.5.12.4 Confidentiality

Given the sensitive nature of genetic data, Roche has implemented additional processes to ensure patient confidentiality for RCR specimens and associated data. Upon receipt by the RCR, each specimen is "double-coded" by replacing the patient identification number with a new independent number. Data generated from the use of these specimens and all clinical data transferred from the clinical database and considered relevant are also labeled with this same independent number. A "linking key" between the patient identification number and this new independent number is stored in a secure database system. Access to the linking key is restricted to authorized individuals and is monitored by audit trail. Legitimate operational reasons for accessing the linking key are documented in a standard operating procedure. Access to the linking key for any other reason requires written approval from the Pharma Repository Governance Committee and Roche's Legal Department, as applicable.

Data generated from RCR specimens must be available for inspection upon request by representatives of national and local health authorities, and Roche monitors, representatives, and collaborators, as appropriate.

Patient medical information associated with RCR specimens is confidential and may be disclosed to third parties only as permitted by the Informed Consent Form (or separate

authorization for use and disclosure of personal health information) signed by the patient, unless permitted or required by law.

Data derived from RCR specimen analysis on individual patients will generally not be provided to study investigators unless a request for research use is granted. The aggregate results of any research conducted using RCR specimens will be available in accordance with the effective Roche policy on study data publication.

Any inventions and resulting patents, improvements, and/or know-how originating from the use of the RCR data will become and remain the exclusive and unburdened property of Roche, except where agreed otherwise.

4.5.12.5 Consent to Participate in the Roche Clinical Repository

The Informed Consent Form will contain a separate section that addresses participation in the RCR. The investigator or authorized designee will explain to each patient the objectives, methods, and potential hazards of participation in the RCR. Patients will be told that they are free to refuse to participate and may withdraw their specimens at any time and for any reason during the storage period. A separate, specific signature will be required to document a patient's agreement to provide optional RCR specimens. Patients who decline to participate will not provide a separate signature.

The investigator should document whether the patient has given consent to participate by completing the RCR Research Sample Informed Consent eCRF.

In the event of an RCR participant's death or loss of competence, the participant's specimens and data will continue to be used as part of the RCR research.

4.5.12.6 Withdrawal from the Roche Clinical Repository

Patients who give consent to provide RCR specimens have the right to withdraw their specimens from the RCR at any time for any reason. After withdrawal of consent, any remaining samples will be destroyed or will no longer be linked to the patient. If a patient wishes to withdraw consent to the testing of his or her specimens, the investigator must inform the Medical Monitor in writing of the patient's wishes through use of the RCR Subject Withdrawal Form and, if the trial is ongoing, must enter the date of withdrawal on the RCR Research Sample Withdrawal of Informed Consent eCRF. If a patient wishes to withdraw consent to the testing of his or her RCR samples after closure of the site, the investigator must inform the Sponsor by emailing the study number and patient number to the following email address:

[contact]

A patient's withdrawal from Study WO29636 does not, by itself, constitute withdrawal of specimens from the RCR. Likewise, a patient's withdrawal from the RCR does not constitute withdrawal from Study WO29636.

4.5.12.7 Monitoring and Oversight

RCR specimens will be tracked in a manner consistent with Good Clinical Practice by a quality-controlled, auditable, and appropriately validated laboratory information management system, to ensure compliance with data confidentiality as well as adherence to authorized use of specimens as specified in this protocol and in the Informed Consent Form. Roche monitors and auditors will have direct access to appropriate parts of records relating to patient participation in the RCR for the purposes of verifying the data provided to Roche. The site will permit monitoring, audits, IRB/EC review, and health authority inspections by providing direct access to source data and documents related to the RCR samples.

4.5.13 Timing of Study Assessments

Flowcharts of scheduled study assessments are provided in [Appendix 1](#) and [Appendix 2](#). Patients will be closely monitored for safety and tolerability throughout the study. All assessments must be performed and documented for each patient. Patients should be assessed for toxicity prior to each dose; dosing will occur only if the clinical assessment and local laboratory test values are acceptable. If the timing of a protocol-mandated study visit coincides with a holiday and/or weekend that precludes the visit, the visit should be scheduled on the nearest following feasible date.

4.5.13.1 Screening and Pre-Treatment Assessments

Prior to signing the main consent form for the study, patients may specifically allow for the collection and testing of archival or fresh tumor tissue by signing the pre-screening consent form. Written informed consent for participation in the study (on the main study Informed Consent Form) must be obtained before performing any study-specific screening tests or evaluations. Informed Consent Forms for enrolled patients and for patients who are not subsequently enrolled will be maintained at the study site.

Screening tests and evaluations will be performed within 28 days prior to randomization, unless otherwise specified. Results of standard-of-care tests or examinations performed prior to obtaining informed consent and within 28 days (or as otherwise specified) prior to randomization may be used; such tests do not need to be repeated for screening. All screening evaluations must be completed and reviewed to confirm that patients meet all eligibility criteria before randomization. The investigator will maintain a screening log to record details of all patients screened and to confirm eligibility or record reasons for screening failure, as applicable.

See [Appendix 1](#) for the schedule of screening and pre-treatment assessments.

4.5.13.2 Assessments during Treatment/Observation

All visits must occur within ± 3 days from the scheduled date unless otherwise noted (see [Appendix 1](#)). All assessments will be performed on the day of the specified visit unless a time window is specified. Assessments scheduled on the day of study treatment administration (Day 1) of each cycle should be performed prior to study

treatment infusion unless otherwise noted. Local laboratory assessments from each cycle must be reviewed prior to study treatment administration for each cycle.

See the table provided in [Appendix 1](#) for the schedule of treatment/observation period assessments.

The following assessments may be performed ≤ 96 hours before Day 1 of each cycle: ECOG performance status, limited physical examination, local/central laboratory tests, adverse event evaluation, and concomitant medication evaluation.

For patients in Arm A, if scheduled dosing is precluded because of a holiday, then dosing may be postponed to the soonest following date, with subsequent dosing continuing on a 21-day schedule. If treatment was postponed for fewer than 2 days, the patient can resume the original schedule. For patients in both arms, if scheduled study assessments cannot be obtained because of a holiday, these assessments should then be obtained at the soonest following date, provided that the soonest following date is not within 2 days of other regularly scheduled study assessments.

Assessments for disease recurrence should continue to occur as specified in Section [4.5.5](#), regardless of treatment delays.

After five cycles have been completed, one cycle may be delayed by 1 week (i.e., 28 days instead of 21 days for one cycle) for one time to allow for vacations.

Blood samples for pharmacodynamic biomarker analysis and pharmacokinetics will be obtained for patients in Arm A according to the schedule in [Appendix 2](#).

4.5.13.3 Assessments at Treatment/Observation Discontinuation Visit

Atezolizumab-treated patients (in Arm A) who discontinue early from treatment or who complete the study treatment in full (16 cycles or 1 year, whichever occurs first) will be asked to return to the clinic not more than 30 days after the last treatment for a treatment discontinuation visit. The visit at which the decision is made to discontinue treatment (e.g., disease recurrence is determined or confirmed) may be used as the treatment discontinuation visit.

Patients randomized to observation (in Arm B) and who discontinue early from the observation period or who complete observation in full (16 cycles or 1 year, whichever occurs first) will also be asked to return to the clinic not more than 30 days after the last cycle visit for an observation discontinuation visit. The visit at which the decision is made to discontinue patient from the observation period (e.g., disease recurrence is determined or confirmed) may be used as the observation discontinuation visit.

See [Appendix 1](#) and [Appendix 2](#) for the schedule of assessments performed at the treatment/observation discontinuation visit.

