4.6.2 Adverse Events

All adverse events, regardless of attribution, will be recorded until 30 days after the last dose of study drug (for patients in Arm A) or 30 days after the last day of the observation period (for patients in Arm B), or the initiation of another anticancer therapy, whichever occurs first. Serious adverse events (see Section 5.2.2) and protocol defined adverse events of special interest (see Section 5.2.3) will be recorded until 90 days after the last dose of study drug or until the initiation of another anti-cancer therapy, whichever occurs first (for patients in Arm A).

After the treatment/observation discontinuation visit, adverse events should be followed as outlined in Section 5.6.

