5.3.1 Adverse Event Reporting Period

Investigators will seek information on adverse events at each patient contact. All adverse events, whether reported by the patient or noted by study personnel, will be recorded in the patient’s medical record and on the Adverse Event eCRF.

After informed consent has been obtained **but prior to initiation of study drug** for patients in Arm A or prior to the Cycle 1, Day 1 visit for patients in Arm B, only serious adverse events caused by a protocol-mandated intervention (e.g., invasive procedures such as biopsies, discontinuation of medications) should be reported (see Section 5.4.2 for instructions for reporting serious adverse events).

For patients in Arm A, after initiation of study drug, all serious adverse events and adverse events of special interest, regardless of relationship to study drug, will be reported until 90 days after the last dose of study drug or until the initiation of another anti-cancer therapy, whichever occurs first. All other adverse events, regardless of relationship to study drug, will be reported until 30 days after the last dose of study drug or until the initiation of another anti-cancer therapy, whichever occurs first.

For patients in Arm B, all adverse events occurring from the date of the Cycle 1, Day 1 visit until 30 days after the last day of the observation period or until the start of an anti-cancer therapy (whichever occurs first) will be reported.

Instructions for reporting adverse events that occur after the adverse event reporting period are provided in Section 5.6.

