5.6 ADVERSE EVENTS THAT OCCUR AFTER THE ADVERSE EVENT REPORTING PERIOD

After the end of the adverse event reporting period (see Section 5.3.1), all deaths, regardless of cause, should be reported through use of the Survival Follow-Up eCRF. In addition, if the investigator becomes aware of a serious adverse event that is believed to be related to prior study drug treatment or study procedure, the event should be reported through use of the Adverse Event eCRF. However, if the EDC system is not available, the investigator should report these events directly to the Sponsor or its

designee, either by faxing or by scanning and emailing the paper Clinical Trial Serious Adverse Event/Adverse Event of Special Interest Reporting Form using the fax number or email address provided to investigators.

5.7 EXPEDITED REPORTING TO HEALTH AUTHORITIES, INVESTIGATORS, INSTITUTIONAL REVIEW BOARDS, AND ETHICS COMMITTEES

The Sponsor will promptly evaluate all serious adverse events and adverse events of special interest against cumulative product experience to identify and expeditiously communicate possible new safety findings to investigators, IRBs, ECs, and applicable health authorities based on applicable legislation.

To determine reporting requirements for single adverse event cases, the Sponsor will assess the expectedness of these events using the following reference document:

- Atezolizumab Investigator's Brochure

The Sponsor will compare the severity of each event and the cumulative event frequency reported for the study with the severity and frequency reported in the applicable reference document.

Reporting requirements will also be based on the investigator's assessment of causality and seriousness, with allowance for upgrading by the Sponsor as needed.

An iDMC will monitor the incidence of these expected events during the study. An aggregate report of any clinically relevant imbalances that do not favor the test product will be submitted to health authorities.

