Appendix 1 Schedule of Assessments (cont.)

Study Procedures	Both Arms	Arm A (Atezolizumab)		Arm B (Observation)			Both Arms
	Screening for Randomization	All Cycles	Discontinuation ^a	Cycles 1, 3, 5, 7, 9, 11, 13, and 15	Cycles 2, 4, 6, 8, 10, 12, 14, and 16	Discontinuation ^a	Follow-Up
	Days –28 to –1	Day 1 (± 3 Days for Cycles ≥ 2) ^b	≤ 30 Days after Last Dose	Day 1 (± 3 Days for Cycles ≥ 2) ^b	Day 1 (± 3 Days) ^b	≤ 30 Days after Last Visit	
Adverse events ^x	x	x	x	x	x	x	
Telephone contact ^y					x		
Survival and anticancer therapy follow-up ^z							x
Patient-reported outcomes ^{aa}		x ^{bb}	x	x		x	x

Note: For Arm A, assessments scheduled on the days of study treatment infusions should be performed before the infusion unless otherwise noted.

- ^a Patients will be asked to return to the clinic for a discontinuation visit not more than 30 days after the decision to discontinue treatment/observation early, or after the end of the one-year treatment/observation period.
- ^b After five cycles have been completed, one cycle may be delayed by 1 week (i.e., 28 days instead of 21 days for one cycle) for one time to allow for vacations.
- ^c Written informed consent is required for performing any study-specific tests or procedures. Written informed consent (on the main study Informed Consent Form) can be obtained outside the 28 days screening period prior to randomization. Prior to signing the main consent form for the study, patients may specifically allow for the collection and testing of archival or fresh tumor tissue by signing the pre-screening consent form. Results of standard-of-care tests or examinations performed prior to obtaining informed consent and within 28 days prior to randomization (except where otherwise specified) may be used for screening assessments rather than repeating such tests.
- ^d Cancer history includes stage, date of diagnosis, and prior anti-tumor treatment. Demographic information includes sex, age, and self-reported race/ethnicity.
- ^e Serum pregnancy test (for women of childbearing potential, including women who have had a tubal ligation) must be performed and documented as negative within 14 days prior to Cycle 1 Day 1. Starting from Cycle 3, either serum or urine pregnancy test (positive urine test results will be confirmed with a serum pregnancy test) must be performed every two cycles during the study treatment, and as clinically indicated thereafter.

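### Section 4.6.2 hands Arm A adverse events to Section 5.6 at the discontinuation visit, although the SAE/AESI reporting period runs to Day 90 after the last dose

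*Protocol*

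**What the plan says.** Protocol Section 5.3.1 sets the Arm A reporting period. All SAEs and AESIs, "regardless of relationship to study drug, will be reported until 90 days after the last dose of study drug" or until another anti-cancer therapy starts, if that is sooner; other adverse events run to 30 days. Section 4.6.2 gives the same 90-day rule and then ends: "After the treatment/observation discontinuation visit, adverse events should be followed as outlined in Section 5.6".

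Section 5.6 begins at the end of the Section 5.3.1 reporting period. From then on it requires all deaths regardless of cause and, beyond deaths, a report "if the investigator becomes aware of a serious adverse event that is believed to be related to prior study drug treatment or study procedure".

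Section 4.5.13.3 times the visit: Arm A patients "will be asked to return to the clinic not more than 30 days after the last treatment for a treatment discontinuation visit". It may be earlier, because the visit where stopping is decided can serve in its place. Appendix 1 footnote a times the same visit differently, at "not more than 30 days after the decision to discontinue treatment/observation early, or after the end of the one-year treatment/observation period".

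In the Appendix 1 schedule, the row "Adverse events ^x" is marked at screening, at the cycle visits and at the discontinuation visits. It has no mark under Follow-Up.

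**The concern.** Two consecutive sentences of Section 4.6.2 cannot both be followed. One keeps full SAE/AESI recording open to Day 90. The other narrows the scope at a visit that may come 60 to 90 days earlier. A site that works from the last sentence and from the schedule table could stop recording two kinds of event after the visit: non-fatal SAEs judged unrelated, and AESIs that are not serious. The AESI list in Section 5.2.3 includes conditions that are often non-serious, such as hypothyroidism and Grade 2 cardiac disorders.

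SAEs and AESIs are planned safety summaries (Protocol Section 6.5, SAP Section 4.5.2). Neither section's definition of a treatment-emergent event sets a cut-off after the last dose, so the reported Arm A rates depend on what sites collect in this period. Any loss would make atezolizumab look safer than it is.

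**Working it through.** The documents give no summary figure to reproduce. The check sets the sections side by side and counts days after the last dose (Day 0).

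**1. When each rule starts and stops (Arm A SAEs/AESIs)**
- Section 5.3.1: full scope to Day 90.
- Section 4.6.2, 90-day sentence: full scope to Day 90.
- Section 4.6.2, last sentence: Section 5.6 scope from the discontinuation visit, Day 0 to Day 30 under Section 4.5.13.3.
- Section 5.6: narrower scope only after the Section 5.3.1 period, so after Day 90.

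The last sentence of Section 4.6.2 therefore disagrees with the sentence before it, with Section 5.3.1, and with the section it points to.

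**2. Window left after the last visit marked for adverse events** (90 minus visit day)
- Visit at Day 30: 90 − 30 = 60 days (60/90 = 67%).
- Visit at Day 21, for example when stopping is decided at the next cycle visit: 90 − 21 = 69 days (77%).
- Visit at Day 0: 90 days (100%).

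**3. Effect of footnote a**
- On-schedule completer: Cycle 16 Day 1 is 15 × 21 = 315 days after Cycle 1 Day 1. A visit up to 30 days after the end of the year is at most (365 − 315) + 30 = Day 80, leaving 10 days.
- Stopping decided after a 42-day hold (Section 5.1.3): 42 + 30 = Day 72, leaving 18 days.

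So the 60-day figure holds under Section 4.5.13.3 and the Appendix 1 column header, but not under footnote a.

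**4. Other scheduled contacts, on-schedule completer without recurrence**
- Recurrence assessments at Weeks 48 and 60. If the first dose is on the day of randomization, 336 − 315 = Day 21 and 420 − 315 = Day 105, each ± 7 days. If the first dose is 7 days later, Day 14 and Day 98, each ± 7.
- ATA/PK sample: 120 ± 30, so Day 90 to Day 150.
- First survival contact, 3 months ± 7 days: about Day 84 to 98 counted from the last dose, or Day 114 to 128 counted from a Day 30 visit. Section 4.6.4 lets it be done from medical records.

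For this patient no scheduled contact need fall between Day 30 and Day 90, but contacts soon afterwards could collect the window in retrospect.

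**5. Other scheduled contacts, early stoppers**
- Recurrence found at Day 21: EQ-5D-5L telephone interviews at 6 and 12 weeks fall at 21 + 42 = Day 63 and 21 + 84 = Day 105.
- No recurrence: assessments continue every 84 days. If stopping time is uniform over that interval (an assumption), about 60/84 = 71% have one between Day 30 and Day 90.

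**The case against.** The best defence is that the 90-day duty is plain and repeated. It stands in Sections 4.6.2, 5.1, 5.1.2.2, 5.3.1 and 5.4.2.2 and in Appendix 1 footnote x, which is attached to the adverse-event row itself. Section 5.6 limits itself to the time after the reporting period, so an investigator who follows the cross-reference reaches a rule that does not yet apply. Section 5.3.1 also tells investigators to ask about adverse events at every patient contact, and the contacts in steps 4 and 5 of the working are such occasions. Relaxing assessments after the primary analysis changes little: an on-schedule window closes about 315 + 90 = 405 days after Cycle 1 Day 1, while that analysis is projected about 18 months after enrolment ends (Month 50 against Month 32).

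Most of this stands, and it rules out several stronger readings. A reader might infer that the 90-day window is simply not delivered; the repeated duty and the later contacts do not support that. Nor does Section 4.6.2 move to related SAEs alone, because Section 5.6 also takes all deaths. A reader might scale the gap to about 400 × 60 / 365.25 = 65.7 patient-years without an adverse-event contact. That ignores the contacts above, deaths, withdrawals, new therapy that closes the window, and footnote a. A reader might also expect early stoppers to be the worst covered, but step 5 shows they often have a contact inside the window, whereas on-schedule completers may not.

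The defence does not remove the conflict. Section 5.1.2.2 and footnote x speak of following patients who have had an event, which can be read as follow-up of known cases rather than a search for new ones. Collection at the later contacts is an inference from Section 5.3.1; no schedule entry calls for it. A survival update taken from records is not a patient contact.

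**Conclusion.** The inconsistency is real and worth correcting. Its consequence is a risk of under-counting unrelated non-fatal SAEs and non-serious AESIs in Arm A between the discontinuation visit and Day 90. Under Section 4.5.13.3, 60 to 90 of the 90 days follow the last visit marked for adverse events (60 with a Day 30 visit); under footnote a the remainder could be as short as 10 to 18 days in the cases worked. These are days without a designated assessment, not days of lost data, and the documents give no basis for estimating how many events would be missed.

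The conclusion assumes that the Follow-Up cell is truly blank. The extracted table shows six marks for seven columns, the SAP copy of the schedule shows the same, and the survival and patient-reported outcome rows do carry a Follow-Up mark, so this is the likely reading. New anti-cancer therapy ends the window earlier by rule and shortens the exposed time for those patients. Efficacy analyses are not affected.

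**What to change.** - In Section 4.6.2, reword the opening of the last sentence to: *After the adverse event reporting period defined in Section 5.3.1*. This removes the conflict with Sections 5.3.1 and 5.6.
- In Appendix 1, mark the adverse-event row under Follow-Up for Arm A. State that SAEs and AESIs through Day 90 (or new anti-cancer therapy) are collected at an existing contact made with the patient at or after Day 90: the ATA/PK visit, or the first survival contact if it is not taken from records alone.
- Reconcile the timing of the discontinuation visit between Section 4.5.13.3, which counts from the last treatment, and Appendix 1 footnote a, which counts from the decision or the end of the year.

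The documents do not say how many Arm A patients are still inside the window. For those already past it, sites can be queried in retrospect and the limitation stated in the study report.

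The cost is a wording change, a few questions at a contact already planned, and slightly more site work. The reported Arm A event rate may rise somewhat.
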